9.7.2. Pregnancy

Each female subject should be instructed to inform the investigator immediately if she becomes pregnant at any time between the start of study screening until 30 days after the last administration of study drug. Similarly, a male subject should also be instructed to inform the investigator immediately if his female partner becomes pregnant during the same study period.

The investigator should counsel the subject regarding the possible effects of study drug exposure on the fetus and the need to inform the study center, the medical monitor, and the sponsor (or designee) of the outcome of the pregnancy.

Neither the pregnancy itself nor an induced elective abortion to terminate the pregnancy without medical reasons is considered an AE; such occurrences should be reported on the appropriate pregnancy report forms. However, if the outcome of the pregnancy meets the criteria for classification as an SAE (ie, spontaneous abortion, induced abortion due to complications, stillbirth, neonatal death, or congenital anomaly [including that in an aborted fetus]), the investigator should follow the procedures for reporting SAEs (ie, report the event to the sponsor [or designee] and follow up by submission of the appropriate AE eCRFs (see Section 9.7.1).

Additional information about pregnancy outcomes that are classified as SAEs includes:

- Any spontaneous abortion, including miscarriage and missed abortion, will be reported as an SAE.
- An induced therapeutic abortion to terminate any pregnancy due to complications or other medical reasons will be recorded as an SAE. The underlying medical reason for this procedure should be recorded as the AE term.
- All neonatal deaths that occur within 1 month of birth should be reported, without regard to causality, as SAEs. In addition, any infant death after 1 month that the investigator assesses as possibly related to the in-utero exposure to the study drug should also be reported.
- In the case of a live birth, the "normality" of the newborn can be assessed at the time of birth (ie, there is no required minimum follow-up of a presumably normal infant before the pregnancy outcome report eCRF can be completed).
- The "normality" of an aborted fetus can be assessed by gross visual inspection unless there are pre-abortion laboratory findings suggestive of a congenital anomaly, in which case pathologic examination should be requested.

Information regarding any pregnancy in a study subject or the female partner of a male subject must be documented on a pregnancy report form and forwarded to the sponsor (or designee) for contact list) within 24 hours of becoming aware of the pregnancy. Monitoring of the pregnancy in both female study subjects and female partners of male study subjects should continue until the conclusion of the pregnancy. For female partners of male study subjects, such monitoring

applies if the pregnancy occurs in the period from the subject's start of study drug until 30 days after the subject's last dose of study drug. The outcome of the pregnancy should be reported on the pregnancy outcome report form within 5 days of the conclusion of the pregnancy. If the end of the pregnancy occurs after the study has been completed, the outcome should be reported to the sponsor (or designee).

9.7.3. Contact Information for Reporting an SAE or Pregnancy

Contact information for reporting an SAE or Pregnancy will be managed by the CRO.

9.8. Sponsor Reporting Requirements

Each SAE or special situation report received from the investigator will be evaluated by the sponsor (or designee). The sponsor (or designee) will assess the seriousness of the event (see Section 9.1.2), the expectedness of the event (see Section 9.1.3), and the relationship to participation in the study (see Section 9.5). The sponsor (or designee) will also indicate whether there is concurrence with the details of the report provided by the investigator.

The sponsor (or designee) will provide information for reporting of suspected, unexpected, serious adverse reactions (SUSARs) to regulatory authorities worldwide consistent with relevant legislation or regulations, including the applicable US FDA CFR, the European Commission Clinical Trials Directive (2001/20/EC, and revisions), and other country specific legislation or regulations. SUSARs will be reported to regulatory authorities within 7 calendar days for life threatening and fatal events, or 15 calendar days for all others. These timeframes begin with the first notification of the event from the reporting investigator to the sponsor (or designee), which represents the start of the regulatory clock (Day 0).

The sponsor (or designee) will also provide all investigators with a safety letter describing the SUSAR. The information will be provided by e-mail, fax, or overnight mail within 15 calendar days from Day 0. Investigators will be requested to provide written notification of the event to the relevant IRB/IEC as soon as is practical and consistent with local regulatory requirements and local institutional policy.

Hematology	Hematocrit, hemoglobin, erythrocyte count, absolute counts of leukocytes, neutrophils, lymphocytes, monocytes, eosinophils, basophils Platelet count			
Laboratory – Pharmacok	inetic ¹			
Plasma pharmacokinetics	Plasma LAM-002A concentrations (as assessed by validated bioassays) (Worldwide Clinical Trials Early Phase Services/Bioanalytical Sciences, LLC., [name].) Retention of plasma for potential metabolite analyses			
Laboratory – Pharmacod	ynamic ¹			
Peripheral blood and	Plasma cytokines might be analyzed for levels of IL-12, IL-23, IL-6, IFN-γ, IL-10 and GM-CSF (additional cytokines may be analyzed in parallel)			
cellular pharmacodynamics	Target engagement biomarkers might be assessed via RNA-seq or qRT-PCR from RNA isolated from nasopharyngeal swabs and PBMC, or in plasma via established Luminex and or ELISA assays			
Laboratory – Disease-rela	ited			
SARS-CoV-2 assessments	Nasopharyngeal swab and saliva to determine SARS-COV-2 viral load using a qRT-PCR method.			
SARS-CoV-2 mutational analysis	Mutational profiling of SARS-CoV-2 viral genome might be analyzed by RNA-seq or comparable technology ¹			
Genetic Polymorphism in COVID-19 subjects	Analysis of germline DNA sequence polymorphisms in genomic DNA isolated from blood or Nasopharyngeal swabs ¹			
Other				
Body weight/height	Weight in kilograms, height in centimeters			
Body temperature	Temperature in degrees Celsius			
Blood pressure	Diastolic and systolic blood pressure in mm Hg			
Oxygen saturation	% saturation			
12-lead ECG	Heart rate, cardiac intervals, wave form abnormalities, ectopy			

Table 0. Laboratory and Other Parameters to be Assessed

Abbreviations: ALP=alkaline phosphatase, ALT=alanine aminotransferase, AST=aspartate aminotransferase, BUN=blood urea nitrogen, CK=creatine kinase, DNA=deoxyribonucleic acid, ECG=electrocardiogram, LDH=lactate dehydrogenase, PCR=polymerase chain reaction, RNA=ribonucleic acid.

¹Samples will be collected for pharmacokinetic, immunogenicity, and genetic exploratory end points. The analysis for these exploratory endpoints is optional

10.2. Sample Shipping, Storage, and Retention

Routine clinical safety samples (for pregnancy test, serum chemistry, and hematology) will be analyzed at the clinical laboratory at the study center and will not be shipped. These samples will not be stored and will be discarded promptly after analysis. Other samples (viral nasopharyngeal swab samples; saliva; plasma for pharmacokinetics; blood and plasma for pharmacodynamics) will be prepared following the instructions outlined in a detailed clinical study laboratory manual.

These samples will be shipped to the sponsor or the contract analytical laboratories using a shipping service designated by the sponsor and as specified in the clinical study laboratory manual. For the duration of the sample analysis campaign, samples will be stored at these contract laboratory facilities or sent for long-term storage at a storage facility designated by the sponsor. Samples will be retained as described for study records (see Section 13.7).

As described for other study records (see Section 13.7), copies of data relating to body weight and height, vital signs, oxygen saturation, etc. will be retained on file at the study centers. The sponsor may request copies of primary ECGs or radiography images (redacted of subject personal identifying information) for storage at the company.

11. EFFICACY ASSESSMENTS

11.1. Primary Efficacy Endpoint: Viral Clearance at Day 4

The primary efficacy outcome measure evaluates SARS-CoV-2 viral load at Day 4 for LAM-002A or placebo-treated subjects. SARS-CoV-2 viral load will be measured in nasopharyngeal specimens by a qRT-PCR method. Analysis will focus on log_{10} viral load on Day 4 adjusted for baseline viral load at Day 1 in subjects with baseline viral load >10⁵ copies/mL.

11.2. Secondary Efficacy Endpoint

11.2.1. Clinical Efficacy

An additional secondary efficacy endpoint measures the proportion of subjects treated with LAM-002A who progressed to hospitalization or who died at Day 28 of randomization compared to those in the placebo arm.

The need for referral for consideration for hospitalization will be assessed based on the CDC guidelines for presentation of mild/moderate, severe, and critical disease

- Mild to moderate: mild symptoms (fever [temperature ≥100.4], cough, sore throat, anosmia, malaise, headache, or muscle pain, gastrointestinal symptoms) up to mild pneumonia
- Severe: dyspnea, hypoxia, or >50% lung involvement on imaging
- Critical: respiratory failure, shock, or multiorgan system dysfunction

Severe and critical disease require hospitalization.

The National Early Warning Score (NEWS) has demonstrated an ability to discriminate patients who are at risk of poor outcomes (Smith et.al., 2015), and has been recommended by the World Health Organization (WHO, 2020). This score is based on 7 clinical parameters. The vital sign scores as measured by the NEWS (Table 1) provides measures of dyspnea, hypoxia as well as other vital signs important to COVID-19 symptoms such as temperature and blood pressure.

Vital signs related to COVID-19 illness will be monitored as specified in Table 7. A composite score of vital sign parameters is calculated at baseline and at each visit. Change of NEWS from baseline will be used to assess resolution or progression of disease and decision for hospitalization.

The following criteria will be used to determine need for hospitalization:

- A composite NEWS >6, or
- One NEWS parameter score of 3 (e.g. RR≥25, Oxygen saturation <91), or
- Respiratory failure, or
- Severe presentations of other COVID-19 symptoms, or
- ECOG Status (see table in Section 15.3)

If the NEWS score increases during the follow-up visits, the subject will be followed more closely with subsequent day tele-health visits until the NEWS score improves or subject further declines, requiring hospitalization.

PHYSIOLOGICAL PARAMETERS	3	2	1	0	1	2	3
Respiration Rate	≤8		9 - 11	12 - 20		21 - 24	≥25
Oxygen Saturations	≤91	92 - 93	94 - 95	≥96			
Any Supplemental Oxygen		Yes		No			
Temperature	≤35.0		35.1 - 36.0	36.1 - 38.0	38.1 - 39.0	≥39.1	
Systolic BP	≤90	91 - 100	101 - 110	111 - 219			≥220
Heart Rate	≤40		41 - 50	51 - 90	91 - 110	111 - 130	≥131
Level of Consciousness				А			V, P, or U

Table 7National Early Warning Score (NEWS)

Level of consciousness = alert (A), and arousable only to voice (V) or pain (P), and unresponsive (U).

NEWS Composite Score

- NEWS = 0-4 Low score: Assessment by a competent registered nurse who should decide if a change to frequency of clinical monitoring or an escalation of clinical care is required.
- NEWS = 5-7 Medium Score: Urgent review by a clinician skilled with competencies in the assessment of acute illness.
- NEWS \geq 7 High Score: Emergency assessment by a clinical/critical care outreach team with critical-care competencies and usually transfer of the patient to a higher dependency care area.

11.2.2. Hospitalization: Clinical Status

The secondary efficacy endpoint evaluates COVID-19 clinical status including subjects who become hospitalized and continue LAM-002A/placebo treatment. Clinical status is defined by the ordinal scale. For subjects (who have the same ordinal score), control versus experimental arms will be compared based on percentage of subjects at each score on Day 28.

COVID-19 Severity Ordinal Scale scores in LAM-002A-treated and placebo-treated subjects will be determined at Day 28 based on the following scores:

- 1. Not in the hospital
- 2. Hospitalized, requiring low flow supplemental oxygen (such as nasal cannula)
- 3. Hospitalized, not on invasive ventilation (such as 100% non-rebreather, BIPAP), (pre-ICU)
- 4. Hospitalized, in the ICU, on invasive ventilation or ECMO
- 5. Dead

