12.4.4.2. Clinical Status (Disease Progression)

The distribution of ordinal scale severity results will be summarized by treatment arm as percentages in the ITT population. A proportional odds model will be used to compare groups on this ordinal scale. The common odds ratio measures the effect size and is valid under the proportional odds assumption that will be verified via a goodness of fit likelihood ratio test. The model will include fixed effects for treatment, and age. Hypothesis tests for the model are nearly identical to the Wilcoxon Rank Sum test. Supportive analysis of this outcome will use the antiviral efficacy analysis population and the PP population.

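### The five-level clinical status scale is neither exhaustive nor mutually exclusive: inpatients without oxygen, and ICU patients on a non-rebreather or BIPAP, have no clear score

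*Combined protocol and SAP*

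**What the plan says.** Section 11.2.2 fixes the time point and the scale: "COVID-19 Severity Ordinal Scale scores in LAM-002A-treated and placebo-treated subjects will be determined at Day 28 based on the following scores". The levels are:

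- Level 1: "Not in the hospital"
- Level 2: "Hospitalized, requiring low flow supplemental oxygen (such as nasal cannula"
- Level 3: "Hospitalized, not on invasive ventilation (such as 100% non-rebreather, BIPAP), (pre-ICU"
- Level 4: "Hospitalized, in the ICU, on invasive ventilation or ECMO"
- Level 5: death

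Section 4.2.3 lists the same five levels, so neither section completes the other. Neither has a rule for a patient who fits no level or more than one.

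Section 12.4.4.2 gives the analysis: "A proportional odds model will be used to compare groups on this ordinal scale". It uses the ITT population with treatment and age as fixed effects, and also tabulates percentages by level. Section 12 leaves full statistical detail to a statistical analysis plan. The text supplied contains no scoring rule.

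**The concern.** An ordinal scale needs exactly one level for every patient, and the levels must run in order of severity. A proportional odds model uses nothing about the levels except their order. If a possible state has no level, someone must choose one at coding. If a state is placed on the wrong side of its neighbour, the model counts a milder outcome as a worse one.

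The unlisted state can occur here. The criteria for hospitalisation in 11.2.1 include "One NEWS parameter score of 3 (e.g. RR≥25, Oxygen saturation <91), or" and "Severe presentations of other COVID-19 symptoms, or". By Table 7, a single parameter score of 3 can come from systolic pressure, heart rate, low temperature or level of consciousness, none of which implies a need for oxygen. ECOG status is a further listed criterion. Section 12.4.4.3 also names respiratory assistance and hospitalisation as separate conditions, so the plan itself does not equate being in hospital with needing respiratory support.

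**Working it through.** The plan states no figure on this point, so the main check is a mapping of states to levels.

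**Step 1. Map each inpatient state to the wording.** Inputs: the level definitions in 4.2.3 and 11.2.2. The literal reading takes level 3 as in hospital, not invasively ventilated and not yet in the ICU. The narrower reading lets the non-rebreather and BIPAP examples define level 3. Both take level 4 as in the ICU and on invasive ventilation or ECMO.

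| State at Day 28 | Literal reading | Examples define level 3 |
|---|---|---|
| Ward, no oxygen | 3 | none |
| Ward, low-flow oxygen | 2 and 3 | 2 |
| Ward, non-rebreather or BIPAP | 3 | 3 |
| ICU, no oxygen | none | none |
| ICU, low-flow oxygen | 2 | 2 |
| ICU, non-rebreather or BIPAP | none | none |
| ICU, invasive ventilation or ECMO | 4 | 4 |

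The first row fails on both readings: the patient is either ranked above (worse than) level 2 or has no level. The second row is a double fit on the literal reading only. The ICU row for non-rebreather or BIPAP has no level on either reading.

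**Step 2. How many scores carry information.** The documents give no hospitalisation rate. Assuming 2% to 10% of 142 patients are in hospital or dead at Day 28: 142 × 0.02 ≈ 3 and 142 × 0.10 ≈ 14 scores other than level 1. Only those still in hospital without oxygen, or in an ICU on non-invasive support, on that day are affected. That number could be zero.

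**Step 3. Effect on the odds ratio, with assumed counts.** Take 71 per arm and six true states (out of hospital, in hospital without oxygen, low-flow, non-rebreather or BIPAP, invasive, dead). Assume active 66/4/1/0/0/0 and placebo 63/0/5/2/0/1. All four no-oxygen inpatients are deliberately put in the active arm. The proportional odds model with treatment alone gives:

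| Scoring of no-oxygen inpatients | Common odds ratio | 95% CI |
|---|---|---|
| Separate level between 1 and 2 | 0.55 | 0.17 to 1.77 |
| Merged with low-flow (level 2) | 0.58 | 0.18 to 1.85 |
| Level 3, as literally worded | 0.62 | 0.19 to 1.98 |

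The largest shift on the log scale is ln(0.62/0.55) = 0.12. The simple split of level 1 against the rest is 5/71 versus 8/71. Its odds ratio is (5/66)/(8/63) = 0.60, with log standard error √(1/5 + 1/66 + 1/8 + 1/63) = 0.60. The shift is therefore 0.12/0.60 = 0.2 standard errors, and the direction does not change.

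**Step 4. The same counts among hospitalised or dead patients only.** Section 4.2.3 words the endpoint for subjects who become hospitalised and continue treatment, whereas 12.4.4.2 uses ITT. Restricting the assumed counts to the 5 + 8 = 13 patients not at level 1, correct ordering puts the active arm at the milder end, with so little overlap that the model gives no stable estimate. Literal scoring gives an odds ratio of 3.36 (95% CI 0.36 to 31), with the active arm appearing worse. This is one constructed case. It shows that a reversal is possible, not that it is likely.

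**The case against.** The strongest reply is that the listed levels do rise in severity, and that the inversion appears only if the reader ignores level 3's own examples. That is correct. A reader might infer that the scale as written ranks less sick patients worse. The documents do not establish this, because with the examples taken as defining level 3 a no-oxygen inpatient has no level rather than a worse one. The coverage gap remains on either reading.

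The ICU gap can also be contested. The pre-ICU tag could describe a tier of severity rather than a bed, and the commas in level 4 could be read as alternatives, which would put every ICU patient there. These readings are possible but less natural, and the need to choose between them is itself the problem. The gap does not cover all non-invasive support: an ICU patient on a nasal cannula still fits level 2.

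On size, a reader might infer that a few misplaced patients would dominate the comparison. The documents supply no count of affected patients, and anyone discharged before Day 28 scores level 1. In ITT most of the information lies in level 1 against the rest, and a no-oxygen inpatient is not level 1 on any reading. Hospitalisation or death is analysed separately in 12.4.4.1 without this scale.

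Finally, section 13.10 promises eCRF completion guidelines, which could settle the coding. They are not in the text supplied, so inconsistent coding between sites is a risk and not a demonstrated fact.

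**Conclusion.** The point holds as a defect of coverage and overlap. The levels are neither exhaustive nor mutually exclusive, and no rule resolves the resulting cases. The rank inversion is conditional on the literal reading of level 3. The ICU gap is conditional on the natural reading of levels 3 and 4.

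The practical effect on the planned ITT model is probably modest: about 0.2 standard errors in an illustration built to be unfavourable, on counts that are assumed and not taken from the documents. The effect could be larger if the comparison were confined to hospitalised patients. Because the endpoint is secondary, this is a worthwhile correction and not a threat to the trial's main conclusion.

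**What to change.** Before unblinding, use one list in 4.2.3 and 11.2.2 in which each patient has exactly one level:

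- Either add a level for patients in hospital who do not require supplemental oxygen, between levels 1 and 2, or reword level 2 to cover hospitalised patients on no or low-flow oxygen.
- Define level 3 as high-flow or non-invasive support, whatever the ward, and drop the pre-ICU tag.
- Define level 4 as invasive ventilation or ECMO, without the location condition.

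The cost is protocol wording and, with the added level, one more eCRF option. The schedule of activities already calls for recording supplemental oxygen use. The downside of a separate level is one more sparse category, which can be merged with level 2 without changing the order. Widening level 2 avoids that but loses the distinction between no oxygen and low-flow oxygen. Recoding after unblinding would be open to challenge as data-driven.

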12. STATISTICAL CONSIDERATIONS

This is a double-blind placebo-controlled trial to determine the superiority of LAM-002A compared to placebo in reducing viral load during a 10-day course of therapy.

COVID-19 patients that fulfill all enrollment criteria and provide informed consent to study participation will have their baseline assessments performed and will be randomized using a permuted block scheme (with variable block size) in a 1:1 ratio to one of the two groups: (1) LAM-002A, or (2) placebo.

The study will include an early evaluation of safety, and an interim analysis. Full details of the statistical methods will be developed and outlined in the statistical analysis plan (SAP) and filed with the study sponsor prior to database lock.

12.1. Statistical Hypotheses

All tests performed will be tests of superiority.

For the primary efficacy endpoint, the hypothesis that LAM-002A results in a reduction in viral load compared to placebo in the subgroup of participants with baseline nasopharyngeal viral load $> 10^5$ copies/mL will be tested.

12.2. Sample Size Determination

The study is designed to have high power at a moderate significance level to detect a signal of benefit for the viral load outcome. The sample size calculation is based on the primary endpoint of interest: log₁₀ respiratory (nasopharyngeal swab) viral load at Day 4 post-randomization.

Given the limited data on the variability of the change in log_{10} viral load, the study is powered based on detecting a moderate standardized effect size of 0.3 using an analysis of covariance (ANCOVA), adjusting for baseline log_{10} viral load. (NOTE: For ANCOVA, the effect size is the standard deviation of the treatment means divided by the pooled standard deviations of the observations. An ANCOVA standardized effect size of 0.3 is equivalent to a Cohen's d of 0.60). To be conservative, a R-squared of 0 between the log_{10} viral RNA at 4-days and baseline log_{10} viral RNA was assumed. With a power of 90%, and a type I error rate of 20% (2-sided), it will be possible to detect the hypothesized 0.3 standardized effect size with 74 total patients – 37 patients per group with a 1:1 randomization. We will enroll a sample size of 142 to assure that a sufficient number of participants with baseline viral load >10⁵ copies/ml. The table below shows the power to detect an effect size of 0.3 given 10% loss to follow-up and various proportions enrolled with baseline viral load >10⁵ copies ml.

	Proportion of Enrolled Participants with >10⁵ copies/ml						
	0.40	0.50	0.60	0.70	0.80	0.90	1.00
Power to Detect Effect Size of 0.3	0.79	0.86	0.91	0.94	0.96	0.97	0.98

Based on available data regarding the distribution of viral load, it is conservatively estimated that \geq 50% of randomized participants will have a baseline viral load $>10^5$ copies/mL. The table above demonstrates that enrolling 142 will provide sufficient power even if the proportion with baseline viral load $>10^5$ copies/ml is as low as 40%. The prevalence of this subgroup will be monitored and adjustments to overall sample size may be made if necessary.

